5.3 Assessments during trial

5.3.1 Imaging: Ultrasound/MRI

- Investigators are required to submit images of Ultrasound scans (as listed below) for review and storage for all infants.
- Standard of care MRI scans may be submitted for review and storage for all infants where available and if performed as standard of care assessment **only**.
- A copy of all ultrasound/MRIs will be kept at the participating unit and will also be sent to UCL where it will be uploaded to the Data Safe Haven (DSH). Images will be pseudonymised by sites, with participant's names and hospital/NHS numbers removed before transfer to UCL. Please see Imaging Transfer Guidelines for further details.

Ultrasound scans:

- At Baseline Visit: The baseline ultrasound scan will be used to confirm eligibility.
- At Post-Operative Follow-Up (t=24-48 hours)

Arm A (Intervention) Post-operative cranial ultrasound: will be carried out within 48 hours of NEL. Post-NEL cranial ultrasound scans will be reviewed

regularly by the TMG at least quarterly, which may provide feedback to the participating centre on operative technique and radiographic outcome. **Arm B (Control)** Post-operative cranial ultrasound: This should be carried out

within 48 hours of temporising device insertion.

At VP Shunt insertion (if required)

MRI Scans:

Where available and when MRI scans are performed as part of standard of care assessment at the timepoints listed below **only**. A copy should be kept at participating sites and sent to UCL for upload to the Data Safe Haven:

- At First Clinical Follow-Up (t=term equivalent +/- 1 month)
- At Unscheduled Visits to Neurosurgical Unit

Other MRI/Ultrasound/CT scans

If an infant undergoes any other MRI, CT, or Ultrasound scans as part of their standard of care in addition to those listed above and where available, these should also be sent to UCL. They will be uploaded to the Data Safe Haven (DSH).

5.3.2 Questionnaires

The infant's parent/guardian(s) should complete the EuroQoL EQ-5D-5L, TNO-AZL TAPQOL, Q-CHAT, BITSEA questionnaires at the timepoints listed below.

A telephone interview with the infant's parent/guardian(s) should be conducted by a member of the research team at site to complete the Adapted Client Service Receipt Inventory (CSRI children version) at 3 -6-,12-, 18- months' and 2 years' corrected age.

Table 3. Questionnaires completed by infant's parent/guardian(s)

	Baseline Visit	3-6* Months Clinical Follow-Up Visit (+/-2 months)	Age 1 Year Clinical Follow-Up (+/- 2 months)	18 Months of Age (+/- 2 months) - (Telepho ne Follow- Up)	2 Years correcte d Age Follow- Up (+/- 2 months)
Adapted Client Service Receipt Inventory (CSRI children version) – (Telephone Interview)		Х	Х	Х	Х
Brief Infant Toddler Social Emotional Assessment (BITSEA)					Х
Quantitative Checklist for Autism in Toddlers (Q-CHAT)					Х
EuroQoL EQ-5D-5L*	Х	X*	Х		Х
TNO-AZL TAPQOL			X		Х

^{*}Please ensure parent/guardian(s) are reminded to complete the EQ-5D-5L at **6-months**. If the visit is scheduled earlier than 6 months, please ask parent/guardian(s) to take this questionnaire away for completion and return by post

* Responses to the EQ-5D-5L must be reviewed during the visit to check for parent/guardian self-reported 'severe' or 'extreme' anxiety and depression. Parents/guardians reporting these symptoms should be signposted to access support from their healthcare provider e.g., their GP.

5.4 Participant Transfers

If a participant moves from the area, every effort should be made for them to be seen at another participating trial site. Access to participant's CRFs will be given to the new site and the parent/legal guardian(s) will need to sign a new consent form. Once this has been done, the new site will take over responsibility for the participant; until this has been completed, responsibility for the participant lies with the original site.

5.5 Early Stopping of Follow-up

Infant's parent/guardian(s) may withdraw from the trial intervention between time of consent and prior to surgery. After this point, the infant will have received the trial intervention or control (depending on the arm they were randomised to).

If a parent/legal guardian(s) chooses to discontinue their infant's participation in the trial, they should always be followed up they should continue to be followed up as closely as possible to the follow-up schedule defined in the protocol, providing they are willing. They should be encouraged and facilitated not to leave the whole trial. If they do not wish to remain on trial follow-up, however, their decision must be respected, and the participant will be withdrawn from the trial completely. The CCTU should be informed of this in writing using the appropriate documentation. Participants stopping early may have a negative impact on trial data integrity and the ability to reach the stated outcome measures. Every appropriate effort will be made by the investigators to encourage participants to agree to completion of the primary outcome assessment.

Data already collected during the infant's participation in the trial will be kept for analysis. Any optional consent e.g., future use of stored samples already collected can be refused when leaving the trial early (but this should follow a discussion).

Parent/legal guardian(s) may change their minds about stopping their infant's trial follow-up at any time and re-consent to participation in the trial.

Participants who cease post-randomisation trial follow-up early will not be replaced.

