- 4. Any change in the participant's condition that in the clinician's opinion justifies the discontinuation of trial follow-up after the surgery has been completed.

Intra-operative discontinuation of the NEL (due to complications or technical difficulties as listed in the operative CRF) does not mandate removal of the participant from the trial. Any subsequent treatment following intra-operative discontinuation of the NEL will be at the treating clinician's discretion.

As participation in the trial is entirely voluntary, the parent/legal guardian(s) may choose to discontinue participation of their infant for trial follow-up and data collection at any time without penalty or loss of benefits to which they would otherwise be entitled. Although not obliged to give a reason for discontinuing participation, a reasonable effort should be made to establish this reason, whilst remaining fully respectful of their rights.

It should be clear to the parent/legal guardian(s) and recorded in the patient notes what aspect(s) of the trial the participant is discontinuing their participation. These could include:

- Early cessation from sample collections
- Early cessation from questionnaires
- Early cessation from further trial follow-up
- Early cessation electronic health record use.

Patients should remain in the trial for the purpose of follow-up and data analysis (unless the parent/legal guardian(s) withdraws their consent from all stages of the trial). If a patient ceases follow-up early, refer to Section 5.5.

Data on patients who stop follow-up early will be kept and included in analyses where possible. Infants that are withdrawn by their parent/guardian(s) after having had their baseline data collected, but prior to randomisation, will be recorded as withdrawals. As they will not have been randomised, they will not count towards the target sample size though their baseline data will still be summarised at the reporting stage. Infants who are withdrawn after they have

undergone surgery (either Arm A NEL with Temporising Device or Arm B Temporising Device alone), will not be able to withdraw from the surgical part of the trial, only from trial follow-up visits. Participant's parent/guardian(s) will be fully advised of this at the time of consent for the trial and the time of consent for the surgical procedure.

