5.1.2 Secondary Outcomes

The secondary outcome measures are:

- 1. Developmental Measures:
 - a. Motor quotient (MQ): Age equivalent motor score of the Bayley IV divided by corrected age at assessment, measured at 2 years' corrected age
 - b. Language quotient (LQ): Age equivalent language score of the Bayley IV divided by corrected age at assessment, measured at 2 years' corrected age
- 2. Other neurological and functional assessments conducted during the 2-year follow-up visit:
 - a. Presence of seizures during the first 2 years and use of anticonvulsant medication at 2 years.
 - Presence of cerebral palsy (+ accompanying Gross Motor Function Classification System (GMFCS) grade and deficit distribution map using the Classification of SCPE
 - c. Assessment of hearing and vision (British Association of Perinatal Medicine classification)
 - d. Parent report:
 - i. Brief Infant Toddler Social Emotional Assessment (BITSEA)
 - ii. Quantitative Checklist for Autism in Toddlers (Q-CHAT)
- 3. Mortality up to 2 years corrected age.
- 4. NEL & VP shunt related outcomes:

- a. Safety of NEL: Number of Adverse Events, where Adverse Events would include (and not limited to) secondary bleeding in the brain, post-operative infections, temporising device survival, mortality, stroke, seizures, electrolyte disturbances, CSF leak, unexpected readmissions or return to theatre.
- b. Number and type of further surgical procedures, including revision of the temporising drainage device (VAD or VSG), addition of a second temporising device, surgery for loculated or isolated ventricles, and revisions of the VP shunt, if implanted, until two years' corrected age. These infants often need multiple shunt revisions during their first two years of life. We will have a separate CRF to record data related to these unexpected presentations and procedures.
- c. Requirement for permanent VP shunt insertion at 6 months' corrected age. (This is at the discretion of the treating team in the participating centre, according to routine clinical care).
- 5. Quality of life and health economic assessments:
 - a. Health-Related Quality of Life (HRQoL) in children: TNO-AZL Preschool Children's Quality of Life (TAPQOL) to be assessed at 12-months and 2 years' corrected age
 - b. HRQoL in primary caregiver: EuroQoL EQ-5D-5L to be assessed at baseline, 6 months, 12 months- and 2 years' corrected age

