6.4.2 Notifications

6.4.2.1 Notifications by the Investigator to CCTU

CCTU must be notified of all SAEs excepting those listed in 6.1.2.1 - unless considered **causally related** to the intervention immediately after site staff become aware of the event (in no circumstances should this notification take longer than 24 hours).

The Foreseeable (expected) SAEs listed in section 6.1.2.1 must be reported within 24 hours of site staff becoming aware of them **if they are considered causally related** to the trial intervention (NEL).

'Foreseeable SAEs' that are **not considered causally related** to the trial intervention (NEL) should be reported within 5 working days using the SAE report form.

All 'Unforeseeable SAEs' i.e., all other SAEs occurring in trial participants which are not detailed in Section 6.1.2.1 should be reported within 24 hours of site staff becoming aware of them using the SAE report form.

All Notifiable AEs (NAEs) listed in Section 6.2 should be reported within 5 working days using the Notifiable Adverse Events (NAE) CRF.

Investigators should notify CCTU of any SAEs and Notifiable Adverse Events (NAEs) occurring from the time of randomisation until 2-year hospital visit follow up. From this point forward the site will not actively monitor SAEs or NAEs.

The SAE form must be completed by the site staff named on the delegation log with this responsibility assigned by the PI. The form should be reviewed and signed off by the investigator (listed on the delegation log) who is responsible for the participant's care with

attention paid to the grading and causality of the event. The responsible investigator should check the SAE form at the earliest opportunity, make any changes necessary and sign. Systems should be in place at the site to enable the investigator to check the form for clinical accuracy as soon as possible.

The minimum criteria required for reporting an SAE are the primary event term, participant's trial specific PIN, date of birth, name of reporting investigator and sufficient information on the event to confirm seriousness. Any further information regarding the event that is unavailable at the time of the first report should be completed as soon as it becomes available.

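### Section 5.5 turns declining trial follow-up into complete withdrawal, which contradicts the separate options in the Protocol Treatment Discontinuation section and leaves no stated basis for collecting later outcomes from records

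*Protocol*

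**What the plan says.** Two sections of the protocol tell sites what to do when a family wants to stop.

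The Protocol Treatment Discontinuation section, which falls between 4.5 and 4.7, takes a graded approach. Sites must make clear and record "what aspect(s) of the trial the participant is discontinuing their participation". Four possibilities are listed: samples, questionnaires, "Early cessation from further trial follow-up", and "Early cessation electronic health record use". The default is that "Patients should remain in the trial for the purpose of follow-up and data analysis", with an exception only where consent is withdrawn from all stages. The section ends this instruction by directing sites to Section 5.5 for anyone who ceases follow-up early.

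Section 5.5 asks that families who discontinue be followed as near to the schedule as they will accept, and be encouraged not to leave altogether. For those who do not wish to remain on trial follow-up, "their decision must be respected, and the participant will be withdrawn from the trial completely". On data it says "Data already collected during the infant's participation in the trial will be kept for analysis". It does not mention collecting anything from records after that point. It does ask investigators to encourage completion of the primary outcome assessment, and it lets parents re-consent later.

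Section 5.1.2 includes among the secondary outcomes "Mortality up to 2 years corrected age", adverse events, further surgical procedures to two years' corrected age, and permanent VP shunt at 6 months' corrected age. Section 6.4.2.1 requires notification of SAEs and notifiable adverse events "occurring from the time of randomisation until 2-year hospital visit follow up".

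**The concern.** One section lets a parent stop visits while leaving record use in place. The other treats the same decision as leaving the trial. Because the graded section refers early stoppers to 5.5, a site that follows the cross-reference arrives at the all-or-nothing rule.

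The outcomes at risk are those that need little or no trial contact: death, shunt insertion, re-operation and serious or notifiable events. VP shunt insertion is a routine-care decision by the treating team. Section 3.6 requires unscheduled returns to the neurosurgical unit to be documented in the medical notes, and Section 7.4 accepts paper notes and electronic health records as source documents. Losing these data from an infant whose parents object only to further visits would be avoidable.

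Parents are told the allocation after surgery (Sections 3.6 and 8.2.3), so the decision to stop could differ between arms. Section 8.3.6 intends all randomised infants to enter the analyses other than the primary one where possible, by intention to treat. Avoidable missing data on mortality, shunt and safety outcomes work against that aim.

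**Working it through.** The protocol gives no figure on this point, so the check is a comparison of the texts.

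1. **Is stopping follow-up distinct from stopping record use?** In the Protocol Treatment Discontinuation section, yes. "Early cessation from further trial follow-up" and "Early cessation electronic health record use" are separate items in one list, and the site must say which applies. A family can therefore choose the first without the second.

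2. **When does an infant leave the trial?** In that section, only when consent is withdrawn from all stages. In 5.5, when the family does not wish to remain on trial follow-up. A family that refuses follow-up but accepts record use stays in under the first rule and is out under the second.

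3. **Which rule operates?** The graded section refers anyone ceasing follow-up early to 5.5. Nothing in 5.5 refers back to the four options.

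4. **Does trial follow-up in 5.5 mean more than visits?** The phrase is slightly wider. However, the Protocol Treatment Discontinuation section describes withdrawal after surgery as withdrawal from follow-up visits only, so a site could fairly apply 5.5 to a parent who is declining visits.

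5. **What data survive under 5.5?** Data already collected. Complete withdrawal, together with a retention clause limited to past data, leaves no stated basis for later collection.

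6. **Which outcomes does this touch?**
   - Mortality: to 2 years' corrected age.
   - Further surgical procedures: to two years' corrected age.
   - Permanent VP shunt: at 6 months' corrected age.
   - SAEs and notifiable events: from randomisation to the 2-year visit (6.4.2.1), with no exception stated for families who stop early. This sits uneasily with complete withdrawal.

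7. **Is there a substitute elsewhere?** Section 5.6 asks for a death form if the site learns of a death, but it is written for families who can no longer be contacted. Section 5.5 has no equivalent for families who decline.

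8. **Does the sample size depend on this?** No. The protocol's 90 evaluable infants inflated for 10% loss give 90 / (1 − 0.10) = 100, as stated in 8.1, and rewording 5.5 leaves that unchanged.

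**The case against.** The strongest reply is that the two sections can be read together. Section 5.5 opens with graded participation, asking for follow-up as close to schedule as the family will accept. Complete withdrawal comes last and could be taken to mean the all-stages case of the other section. Section 5.5 does not expressly forbid record review, 6.4.2.1 makes no exception for early stoppers, and the consent form and withdrawal documentation, which may settle record use, are not available here. All of this is fair. It means that loss of later record data is an inference from the wording rather than an instruction. It does not remove the conflict: the trigger in 5.5 is unwillingness to stay on follow-up, not withdrawal from all stages.

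A reader might infer two stronger points. Neither is supported.

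- **That 5.5 forfeits the 2-year Bayley assessment.** The same paragraph asks for every appropriate effort to have the primary assessment completed, and re-consent is allowed at any time. What can be said is that 5.5 names no status for a family that wants only that assessment. Records could not replace the Bayley score in any case.

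- **That the shunt comparison carries a 10-point band of uncertainty.** This comes from 10% of 50, which is 5 infants per arm, and 5 / 50 = 10 percentage points. But the 10% in 8.1 covers loss to follow-up together with other methodological challenges and is set for the 2-year outcome. Section 5.6 describes loss to follow-up as families who cannot be contacted, not families who decline. The shunt outcome falls at 6 months' corrected age, and Section 1.1 says permanent diversion usually occurs around term-equivalent age, so shunt status would often already be recorded and kept.

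Which families would refuse visits, and whether refusal would favour one arm, is also not documented. Differential withdrawal is possible but has no known direction.

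**Conclusion.** The contradiction is real. Sections 5.5 and Protocol Treatment Discontinuation give different answers for a family that declines follow-up but does not refuse record use, and the cross-reference makes the stricter answer operative. Read literally, 5.5 leaves no stated basis for collecting later mortality, VP shunt, further-surgery and SAE or notifiable-event data from routine records.

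The size of the loss cannot be derived from the protocol. It depends on how many families decline follow-up without objecting to record use, when they do so, and how sites interpret 5.5. The conclusion rests on two assumptions: that sites apply 5.5 as written, and that no other trial document overrides it. The consequences fall on secondary and safety outcomes. The primary analysis and the sample size are not called into question. The change is worth making because it is cheap and prevents avoidable missing data.

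**What to change.** Reword Section 5.5 so that it follows the options already listed in the Protocol Treatment Discontinuation section:

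- A family declining further visits or questionnaires is still offered the 2-year primary assessment.
- If they decline that too, survival, VP shunt, further surgery and SAE or notifiable-event data continue to be collected from routine records to 2 years' corrected age, unless they also refuse record use.
- Complete withdrawal applies only when the parent explicitly withdraws consent from all aspects, including record use.
- The level chosen, and its date, are recorded on the withdrawal documentation.

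The cost is a protocol wording amendment, a field on the withdrawal form if it lacks one, and a small amount of site time for notes review. The parent information sheet and consent form must match the new wording on continued record use. Sample size, primary analysis and clinical care are unchanged.

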5.6 Loss to Follow-up

If a participant's parent/legal guardian(s) is no longer contactable and has missed at least one follow-up visit within the protocol defined visit window (please refer to Participant Timelines for specific follow-up visit windows), then site staff should attempt to contact the participant's parent/legal guardian(s) at least three times over three months before they are declared as lost to follow-up. Attempts should be made to contact the participant's parent/legal guardian(s) via two different methods of contact (i.e., telephone and letter). Site staff may identify and contact the participant's registered GP to obtain up to date contact information and may also contact their paediatrician at their local hospital and/or neonatal unit. A death form should be submitted if the site becomes aware that the patient has died.

5.7 Completion of Protocol Follow-Up

Participants will complete protocol follow-up upon completion of the final visit CRF for the 2-years' corrected age developmental assessment.

6 Safety reporting

The principles of GCP require that both investigators and Sponsors follow specific procedures when notifying and reporting adverse events or reactions in clinical trials. These procedures are described in this section of the protocol. **Section 6.1** lists definitions, **Section 6.3** gives details of the investigator responsibilities and provides information on CCTU responsibilities.

6.1 Definitions

Definitions of harm of the EU Directive 2001/20/EC Article 2 based on the principles of GCP apply to this trial.

Table 4: Definitions

Table 4. Delililions	
Adverse Event (AE)	Any untoward medical occurrence in a study participant,
	which does not necessarily have a causal relationship with
	the study intervention (NEL).
Notifiable Adverse Event	Any AE that:
(NAE)	•is listed in section 6.2 (Notifiable Adverse Events)
	These events should be reported within 5 working days of
	site becoming aware.
Serious Adverse Event	Any AE that:
(SAE)	results in death
	• is life threatening*
	requires hospitalisation or prolongs existing
	hospitalisation**
	results in persistent or significant disability or incapacity
	is a congenital anomaly or birth defect
	or is another important medical condition***
Foreseeable (Expected)	Any AE that:
SAE	results in death
	• is life threatening*
	requires hospitalisation or prolongs existing
	hospitalisation**
	results in persistent or significant disability or incapacity
	is a congenital anomaly or birth defect
	or is another important medical condition***
	AND
	•is listed in section 6.1.2 (Foreseeable Adverse Events)
	These events must be reported within 5 days of site
	becoming aware if there is no causal relationship to trial
	intervention (NEL)
	These events must be reported within 24 hours of site
	becoming aware if causally related to trial intervention
	(NEL).
Unforeseeable	Any AE that:
(unexpected) SAE	results in death
	• is life threatening*
	requires hospitalisation or prolongs existing

hospitalisation**

- results in persistent or significant disability or incapacity
- is a congenital anomaly or birth defect
- or is another important medical condition***

AND

•is **not** listed in section 6.1.2 (Foreseeable Adverse Events)

These events must be reported within 24 hours of site becoming aware if causally related or unrelated to trial intervention (NEL).

- * The term life threatening here refers to an event in which the patient is at risk of death at the time of the event; it does not refer to an event that might hypothetically cause death if it was more severe (e.g., a silent myocardial infarction)
- ** Hospitalisation is defined as an in-patient admission, regardless of length of stay, even if the hospitalisation is a precautionary measure for continued observation. Hospitalisation for pre-existing conditions (including elective procedures that have not worsened) do not constitute an SAE. Hospitalisation for the trial procedure does not constitute an SAE. As infants will be remain in hospital following the trial procedures this specifically refers to additional or prolonged admissions to those expected as per standard of care.
- *** Medical judgement should be exercised in deciding whether an AE is serious in other situations. The following should also be considered serious: important AEs that are not immediately life threatening or do not result in death or hospitalisation but may jeopardise the participant or may require intervention to prevent one of the other outcomes listed in the definition above (e.g., an allergic bronchospasm requiring intensive emergency treatment, seizures or blood dyscrasias that do not result in hospitalisation, or development of drug dependency).

